## 20.0 Other Approvals and Registrations

**20.1 \* ADMINISTRATION OF RECOMBINANT DNA: Does this study involve administration of vaccines produced using recombinant DNA technologies to human subjects (Help Link added Aug '15): (REQUIRED)**

Yes  No

**20.2 \* HUMAN GENE TRANSFER: Does this study involve human gene transfer (NOTE: Requires NIH Recombinant DNA Advisory Committee (RAC) review prior to IRB approval): (REQUIRED)**

Yes  No

**20.4 OTHER APPROVALS: Indicate if this study involves other regulated materials and requires approval and/or authorization from the following regulatory committees:**

Institutional Biological Safety Committee (IBC)

Specify BUA #:

[name] lab: BUA 49187-BU-01-INC; CLIA certificate 05D1024215

Institutional Animal Care and Use Committee (IACUC)

Specify IACUC #:

Controlled Substances

## 21.0 End of Study Application

### 21.1 End of Study Application Form

**To continue working on the Study Application: Click on the section you need to edit in the left-hand menu. Remember to save through the entire Study Application after making changes.**

**If you are done working on the Study Application:**

**Important: Before proceeding, please go back to Section 4.0 Initial Screening Questions and Save and Continue through the form to make sure all the relevant sections and questions have been included. If you've changed any answers since you started, the branching may have changed. Your application will be incomplete and it will have to be returned for corrections.**

**Once you are sure the form is complete, click Save and Continue. If this is a new study, you will automatically enter the Initial Review Submission Packet form, where you can attach consent forms or other study documents. Review the [Initial Review Submission Checklist](#) for a list of required attachments.**

**Answer all questions and attach all required documents to speed up your approval.**

**The UCSF IRB wants your feedback about this new form. Please click the link to take a [brief survey](#) about the new application form.**

#### 4. SUMMARY OF CHANGES TO THE ORIGINAL STUDY PROTOCOL

	Approval date	Summary of modifications
1.2	3/01/16	Initial approval of study application. UCSF as IRB of record, UC Davis and UCLA approved as relying sites.
1.3	5/25/16	
Changes to consent documents:
 
 
removed language that allowed for participants to have the UCSF mNGS test done without participation in the research study. This initial demonstration project will limit access only those who are in the study (meet criteria and are willing to consent).
 
 
Changes to Application:
 
 
section 3- updated study personnel
 
section 7 updated personnel for outside site; Syapse
 
section 11 included referral form that we will use to determine eligibility for study
 
 
Attached docs:
 
 
referral survey
 
CITI training certification for new Syapse team member
 
revised consents
 

1.4	6/10/16	Updated study personnel
1.5	6/20/16	
This modification is being submitted because of a glitch in the iRIS system. Our vulnerable populations were accidentally removed from the application. They have been added again here on the new form. Discussion has been had with [name] and [name].
 
Section 1: DAID-> PDAID
 
Section 3: removed [name]
 
Section 5: CIAPM is listed as funding (this has always been the case)
 
Section 6: removed SFGH, this is still in process, will add them at a later date
 
Section 9: changed to No, this has never been true and was an error.
 
Section 10: added justification for enrollment numbers
 
Added minors, pregnant women, non-English speakers, patients unable to consent themselves, and the economically disadvantaged (this was in the original application form, but glitched out with section 9.6 being selected 'yes')
 
Section 11: inclusion of minors
 
Section 12: added UC ReX
 
Section 12: consent method for non-English speakers
 
Section 16: Added where we are obtaining PHI
 
Section 16/ 14: defined PHI, sensitive data
 
Section 18: removed [name]

1.7	8/19/16	
This modification includes changes to the consent documents, the addition of one study personnel, and includes consenting subjects who have been discharged or transferred.
 
Changes to consent:
 
No major changes
 
Minor changes in language, presentation, and organization
 
These changes are being submitted via the request of our UCLA collaborators in hopes it will make the consent more understandable for study participants
 
Changes to application:
 
Section 3: two team members added
 
Section 12: adding consent for patients who have been transferred or discharged
 
Section 18: qualifications for KSP

1.10	2/22/17	
Section 3- updated staff (originally added in study management prior to modification)
 
Section 3.3- added another contact ([name])
 
Section 4.1 3 UCs-> 4UCs (adding UCSD)
 
Section 5.3 This change may have been an error—the P number is now pulled into the application
 
Section 6.3 adding UCSD
 
Section 6.8- checked UCSD
 
Consent form: added UCSD contact info to adult/adolescent form

1.16	8/17/17	
Application:
 
8.4 added provider survey to procedures
 
15.5 updated and detailed re-consent procedure for patients who were enrolled via surrogate
 
Consent Documents:
 
1. Submitting an adult consent form for St Jude (currently only a minors consent form is available for St Jude)
 
Other Study Documents:
 
1-2. Submitting the provider pre and post test result surveys
 
3. Added phone script for re-consent to surrogate
 
4. Added phone script for re-consent to participant
 
5. Added re-consent letter to participants

		6. Added re-consent letter to surrogates 7. Added Status Update Form
1.17	12/18/17	Section 3: removed [name] as study contact, other personnel changes pulled from study management tab Section 7.1 Outside sites—added new coordinator for CNM Other Documents: CITI cert for new CNMC coordinator who will be doing data collection / chart review

## 5. REGULATORY COMMITTEE APPROVALS

The UCSF Clinical Microbiology Laboratory, a CLIA-licensed facility, operates under CLIA with certificate 05D1024215 and undergoes regular inspections by CAP and CLIA. The [name] research laboratory is able to analyze research samples collected from patients under active BUA (Biological Use Authorization) 49187-BU-01-INC.

This was a multisite study with the following IRB approvals:

## 6. STATISTICAL ANALYSIS PLAN

### 6.1. Original Statistical Analysis Plan

This was a one-year, multicenter, prospective cohort study in which subjects were enrolled based on a particular exposure (i.e. idiopathic meningitis +/- encephalitis and/or myelitis) and then followed over time to assess for the occurrence of the outcome (i.e. results of CSF mNGS testing). Prospective enrollees were identified by physician referral, computerized provider order entry, patient chart review, or screening of daily EMR reports (Supplementary Appendix). Given funding and clinical testing capacity constraints, sample size estimates (n=300) were based on convenience without formal statistical considerations. The target condition was idiopathic meningitis, encephalitis, and/or myelitis in patients undiagnosed at time of enrollment. The index test was the CSF mNGS assay, and the reference standard was a composite of conventional testing and orthogonal confirmatory testing of mNGS-only positive results, either with respect to all clinical testing or direct detection (i.e. non-serologic) testing of CSF only.

Performance measures (sensitivity, specificity, positive predictive value (PPV), and negative predictive value (NPV)) were calculated using standard formulas for proportions, and 95% confidence intervals for these proportions were determined using Wilson's method. The primary analysis was a comparison of the performance of the mNGS assay versus conventional (direct detection) testing using the composite results of direct detection testing of CSF, including orthogonally confirmed mNGS results, as the reference standard. Secondary analyses included 2x2 contingency analyses of other comparative performance measures and calculations of diagnostic yield (the number and proportion of infectious diagnoses made by mNGS or conventional testing).

The original statistical analysis plan may also be viewed as part of original IRB protocol on page 27.

### 6.2. Final Statistical Analysis Plan

This was a one-year, multicenter, prospective cohort study in which subjects were enrolled based on a particular exposure (i.e. idiopathic meningitis +/- encephalitis and/or myelitis) and then followed over time to assess for the occurrence of the outcome (i.e. results of CSF mNGS testing). Prospective enrollees were identified by physician referral, computerized provider order entry, patient chart review, or screening of daily EMR reports (Supplementary Appendix). Given funding and clinical testing capacity constraints, sample size estimates (n=300) were based on convenience without formal statistical considerations. The target condition was idiopathic meningitis, encephalitis, and/or myelitis in patients undiagnosed at time of enrollment. The index test was the CSF mNGS assay, and the reference standard was a composite of conventional testing and orthogonal confirmatory testing of mNGS-only positive results, either with respect to all clinical testing or direct detection (i.e. non-serologic) testing of CSF only.

As gold standard reference results for diagnosis of meningitis and encephalitis was not available (due to the varying extent of diagnostic testing done at each hospital, lack of detailed performance characteristics for each test performed locally, and lack of availability of comprehensive gold standard testing for meningitis and encephalitis), obtaining unbiased estimates of sensitivity and specificity was not possible. Thus, the comparative performance measures of mNGS relative to conventional testing are reported as positive percent agreement (PPA) and negative percent agreement (NPA) to the composite reference standard, in accordance with statistical guidance from the FDA. PPA and NPA were calculated

using standard formulas for proportions, and 95% confidence intervals for these proportions were determined using Wilson's method.

The primary analysis was a comparison of the performance of the mNGS assay versus conventional (direct detection) testing using the composite results of direct detection testing of CSF, including orthogonally confirmed mNGS results. Secondary analyses included 2x2 contingency analyses of the PPA and NPA of the mNGS assay relative to other combinations of conventional diagnostic testing including serology and test results from other tissue types.

The final statistical analysis plan may also be viewed as part of the final IRB protocol on page 78.

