**8.25 STATISTICAL METHODS: Briefly summarize the methods and types of analyses that will be performed:**

The UCSF Clinical Microbiology Laboratory will process the clinical sample under validated standardized operating procedures. Bioinformatics analysis will be performed using the SURPI pipeline (Naccache, et al., 2014). We will also occasionally need to perform orthogonal clinical testing (serological, PCR testing) or research polymerase chain reaction (PCR) testing for confirmation of results. All data will be deidentified prior to submission and submitted to dbGaP (database of Genotypes and Phenotypes), an NIH database which archives deidentified data beyond a controlled-access firewall and makes such data only accessible to a limited number of investigators (see <http://www.ncbi.nlm.nih.gov/sites/entrez?db=gap>).

For the additional excess clinical samples used for research for the purposes of new assay development, we will perform additional analyses including autoantibody profiling, human transcriptome profiling, and probe-based sequencing enrichment.

**8.26 REFERENCES: List only the 5-10 most relevant references (a separate bibliography can be attached for reference purposes if this study involves novel approaches, agents, or an emerging technology that the IRB may not be familiar with):**

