**8.23 DISTRIBUTION: Specimens banked at UCSF may be made available to (check all that apply):**

- UCSF researchers
- Non-UCSF researchers
- Industry
- None of the above - specimens will be retained and used within our own research program

**8.24 UTILIZATION REVIEW: Is there a formal utilization review process for distribution of specimens:** Yes  No**8.25 STATISTICAL METHODS: Briefly summarize the methods and types of analyses that will be performed:**

The UCSF Clinical Microbiology Laboratory will process the clinical sample under validated standardized operating procedures. Bioinformatics analysis will be performed using the SURPI pipeline (Naccache, et al., 2014). We will also occasionally need to perform orthogonal clinical testing (serological, PCR testing) or research polymerase chain reaction (PCR) testing for confirmation of results. Orthogonal testing will be performed to confirm positive mNGS results or by recommendations from the Clinical Microbial Sequencing Board. All data will be deidentified prior to submission and submitted to dbGaP (database of Genotypes and Phenotypes), an NIH database which archives deidentified data beyond a controlled-access firewall and makes such data only accessible to a limited number of investigators (see <http://www.ncbi.nlm.nih.gov/sites/entrez?db=gap>).

For the additional excess clinical samples used for research for the purposes of new assay development, we will perform additional analyses including autoantibody profiling, human transcriptome profiling, and probe-based sequencing enrichment.

**8.26 REFERENCES: List only the 5-10 most relevant references (a separate bibliography can be attached for reference purposes if this study involves novel approaches, agents, or an emerging technology that the IRB may not be familiar with):**

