Over the course of the Precision Diagnosis of Acute Infectious Diseases demonstration project,, each case is discussed with a team of leading experts in neurology, infectious disease and microbiology (CMSB, “clinical microbial sequencing board”). The mNGS findings are put into clinical context, and appropriate treatment and management decisions are recommended to treating physicians. This helps to ensure that proper management decisions are made and that the assay results are interpreted according to the clinical context, thus mitigating risk that may be associated with diagnostics provided outside of the healthcare system associated with the patient.

During the demonstration project, positive findings by mNGS are evaluated using orthogonal testing (clinical testing is preferred if available, or research-based PCR confirmatory testing) to assess the possibility of false-positive results. However, as this assay utilizes significant advances in pathogen detection technology, there is the potential to detect the presence of a pathogen that may not yet be detectable via other diagnostic assays (i.e. detecting a virus before antibody production).

Potential false-negative mNGS results (negative mNGS assay but positive by conventional testing) are also reviewed with additional discrepancy testing performed, as necessary.

The results of the mNGS assay do not solely determine the need for therapy or other patient interventions. Conventional test results and mNGS results are used in the proper clinical context to guide therapy decisions. Given the overall mNGS test performance during clinical laboratory validation studies, expert review and case discussion, and the use of discrepancy testing as needed, the mNGS assay (device) as performed poses a non-significant risk to patients.

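### Do the final SAP and the IRB statistics section set conflicting rules for confirming an mNGS-only positive in the primary analysis?

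*Combined protocol and SAP*

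**What the plan says.** Section 6.2 (Final Statistical Analysis Plan) builds the reference standard from two components: conventional testing, and orthogonal confirmation of results that only mNGS found positive. It gives this composite two possible scopes: "either with respect to all clinical testing or direct detection (i.e. non-serologic) testing of CSF only". The primary analysis takes the narrower one, comparing mNGS with conventional direct detection "using the composite results of direct detection testing of CSF, including orthogonally confirmed mNGS results". Serology and results from other tissues appear among the secondary analyses. The section closes with a pointer: "The final statistical analysis plan may also be viewed as part of the final IRB protocol on page 78". Section 6.1 (Original Statistical Analysis Plan) has the same composite and the same CSF direct-detection primary analysis, with its own pointer: "The original statistical analysis plan may also be viewed as part of original IRB protocol on page 27".

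The only statistical methods section in the final IRB application (version 1.16) is 8.25. On confirmation it says: "We will also occasionally need to perform orthogonal clinical testing (serological, PCR testing) or research polymerase chain reaction (PCR) testing for confirmation of results". It adds: "Orthogonal testing will be performed to confirm positive mNGS results or by recommendations from the Clinical Microbial Sequencing Board". Section 8.25 of the original application (version 1.4) has the same list without the added sentence. In section 9.4 of version 1.16, the argument for non-significant risk, positive mNGS findings are checked by orthogonal testing ("clinical testing is preferred if available, or research-based PCR confirmatory testing"). Section 8.9 allows serum and additional samples such as biopsy to be used for orthogonal work.

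**The concern.** Confirmation decides where an mNGS-only positive falls in the primary 2x2 table. If it is confirmed, the patient is reference-positive and mNGS is credited. If not, the patient counts against negative percent agreement (NPA). Section 6.2 reads as admitting only non-serologic CSF testing to the primary composite. The text it presents as another copy of the plan mentions serology and research PCR and names no specimen. An analyst who took section 8.25 as the rule would count confirmations that section 6.2 leaves out, and each one favours the assay.

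There is a second, narrower worry. Sections 8.25 and 9.4 of version 1.16 distinguish research PCR from clinical testing. Read literally, research PCR on CSF is direct detection of CSF but is not clinical testing. A patient confirmed only in that way would then be positive in the narrow composite and negative in the wide one, so the wide composite would not contain the narrow one.

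**Working it through.** **What each text decides**

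| Question | SAP 6.2 | IRB 8.25 (v1.16 and v1.4) | IRB 9.4 (v1.16) |
|---|---|---|---|
| Defines a reference standard for this trial's analysis? | Yes, two scopes | No | No |
| Names the primary analysis? | Yes, CSF direct detection | No | No |
| Defines agreement measures and intervals? | Yes (PPA, NPA, Wilson) | No | No |
| Lists confirmatory tests? | By type: direct detection of CSF, or all clinical testing | Serology, PCR, research PCR | Clinical testing, else research PCR |
| Assigns a test to an analysis? | Yes; serology and other tissues are secondary | No | No |

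Section 8.25 describes laboratory work across the study. It cannot place a patient in a different cell from section 6.2, because it defines no cells. Its list also fits the structure of section 6.2: PCR on CSF can serve the primary composite, and serology or a non-CSF specimen can serve the wider one.

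**Research PCR.** PCR is non-serologic, so on CSF it is direct detection and fits the primary composite. Section 6.2 names orthogonal confirmation as a component under either scope, and section 9.4 counts research PCR as orthogonal testing. Excluding it from the wider composite requires reading the all-testing set as smaller than its CSF-only subset.

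**Size if the looser reading were used.** The plan has no figure to reproduce: section 6.2 says n=300 was chosen by convenience. Every count below except 300 is assumed.

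- Let P = reference-positives, TP = mNGS-positives among them, C = conventional positives, n = reference-negatives, TN = patients negative on both, and k = mNGS-only positives supported only by serology or a non-CSF specimen.
- Strict rule: NPA = TN/n; mNGS PPA = TP/P; conventional PPA = C/P.
- Loose rule: NPA = TN/(n−k); mNGS PPA = (TP+k)/(P+k); conventional PPA = C/(P+k).
- Base case: P=50, TP=43, n=300−50=250, and 5 other unconfirmed mNGS positives, so TN = 250−5−k.

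| k | NPA strict | NPA loose | mNGS PPA strict | mNGS PPA loose |
|---|---|---|---|---|
| 1 | 244/250 = 97.6% | 244/249 = 98.0% | 43/50 = 86.0% | 44/51 = 86.3% |
| 3 | 242/250 = 96.8% (93.8–98.4) | 242/247 = 98.0% (95.3–99.1) | 86.0% | 46/53 = 86.8% |
| 5 | 240/250 = 96.0% (92.8–97.8) | 240/245 = 98.0% (95.3–99.1) | 86.0% | 48/55 = 87.3% |

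The brackets are Wilson 95% intervals, and they overlap.

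The mNGS-minus-conventional PPA difference is (TP−C)/P under the strict rule and (TP+k−C)/(P+k) under the loose rule:

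- C=40: 3/50 = +6.0 points strict; 4/51 = +7.8 (k=1), 6/53 = +11.3 (k=3), 8/55 = +14.5 (k=5) loose.
- C=45: −2/50 = −4.0 points strict; −1/51 = −2.0 (k=1), 1/53 = +1.9 (k=3), 3/55 = +5.5 (k=5) loose.

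For the literal reading of research PCR, let r of the 50 positives rest on it alone. NPA in the wider composite is then 245/(250+r): 97.6% at r=1, 96.8% at r=3 and 96.1% at r=5, against 245/250 = 98.0%.

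**The case for a change.** The strongest case for a change is that the direction is fixed by algebra. Each extra confirmation raises NPA, raises mNGS PPA unless it is already 100%, and lowers conventional PPA. With C=45, three such patients reverse the sign of the PPA difference. The route is open in practice, since section 8.9 provides for serum and biopsy. The primary sentence in section 6.2 names neither assay nor specimen. Sections 6.1 and 6.2 are undated and in the past tense, section 6.3 records a change of measures made during peer review, and the IRB sections they cite contain no CSF-only rule.

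The arithmetic stands, and so does the observation about the primary sentence. The conclusion does not follow from them. The scope phrase comes after both components of the composite and naturally governs both, and serology and other tissues have their own place among the secondary analyses. On timing, section 6.1 has the same composite and primary analysis, and section 6.3 reports only the move from sensitivity and specificity to PPA and NPA. That does not prove the rule was fixed before results were seen, but the documents show no change to it. Although section 6.2 calls for a comparison with conventional testing, it defines no PPA-difference statistic, which is where the larger movement appears.

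**Conclusion.** No change is needed. Two small points stand: the primary-analysis sentence does not restate which assay or specimen may confirm an mNGS-only positive, and the page-27 and page-78 pointers lead into IRB applications whose statistical sections do not contain the SAP. The first is a gap that an analyst fills correctly from the reference-standard sentence in the same section. The second is a clerical slip.

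Followed on its natural reading, section 6.2 gives a sound primary table: non-serologic CSF testing confirms, including research PCR on CSF, while serology and non-CSF specimens count only in the wider composite. The documents show no effect on results. The illustrative shifts of about 0.4 points of NPA and 2 points of PPA difference per patient rest on assumed counts and on an analyst treating section 8.25 as a reference rule, which it does not claim to be. If no patient depends on serology or a non-CSF specimen alone, both readings give the same table.

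This conclusion assumes that the pointers refer to section 8.25. The table of contents places both pages inside the IRB applications, and the match to 8.25 was made by content.

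### The primary composite accepts conventional CSF positives unconfirmed, so a conventional NPA would be 100% by construction and the mNGS-versus-conventional contrast is one-sided

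*Combined protocol and SAP*

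**What the plan says.** SAP section 6.2 defines the yardstick as follows: "the reference standard was a composite of conventional testing and orthogonal confirmatory testing of mNGS-only positive results". For the primary analysis this is restricted to CSF direct detection: "using the composite results of direct detection testing of CSF, including orthogonally confirmed mNGS results". What is compared is also stated: "The primary analysis was a comparison of the performance of the mNGS assay versus conventional (direct detection) testing using the composite results of direct detection". The measures "are reported as positive percent agreement (PPA) and negative percent agreement (NPA) to the composite reference standard", each with a Wilson 95% interval. Section 6.1 uses the same composite and names its role in the primary analysis outright: "including orthogonally confirmed mNGS results, as the reference standard".

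Two places in the study application, version 1.16, describe follow-up of discordant results. Section 8.25 provides for orthogonal testing to confirm positive mNGS results or on the sequencing board's recommendation. Section 9.4 covers the other direction: "Potential false-negative mNGS results (negative mNGS assay but positive by conventional testing) are also reviewed with additional discrepancy testing performed, as necessary". Neither the SAP nor section 9.4 says whether that second kind of testing can remove a conventional positive from the composite.

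**The concern.** The two tests meet the composite on different terms. A conventional CSF positive is taken as truth on its own; an mNGS-only positive must be corroborated. A conventional false positive therefore cannot appear as an error of conventional testing, whereas an unconfirmed mNGS-only positive always appears as an error of mNGS. The NPA half of a head-to-head would carry no information about which test gives more false positives: mNGS could only tie or lose.

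This matters because NPA is the only specificity-type measure left in the final SAP. Section 6.2 itself says that detailed performance characteristics of the locally performed tests are lacking, so the plan has no basis for treating them as free of false positives. A Wilson interval around the conventional figure would also attach apparent sampling error to a number that cannot vary.

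**Working it through.** There is no planned figure to reproduce. The sample size of 300 is stated to be one of convenience, and no NPA, precision or power figure is given.

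**Algebra.** Let C be a conventional CSF positive, M an mNGS positive and K orthogonal confirmation. The rule in 6.2 gives reference-positive = C, or (M and not C and K). Hence reference-negative implies not C, and:

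- conventional NPA = P(not C | reference-negative) = 1 for any data;
- mNGS NPA = 1 − P(M, not C, not K) / P(reference-negative), which is below 1 as soon as one mNGS-only positive is unconfirmed.

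**Inputs for the size.** N = 300 (6.2). Sensitivity 86.1% and specificity 97.9% for mNGS (validation figures, section 9.4, version 1.16). Assumptions not in the documents: the same accuracy for conventional testing, errors independent given infection status, infection prevalence 35%, all true mNGS-only positives confirmed and no false ones confirmed.

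**Expected cells.** Infected 105, uninfected 195.

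- Reference-negative: 105 × 0.139² + 195 × 0.979 = 2.03 + 190.91 = 192.93.
- mNGS-positive among these: 195 × 0.979 × 0.021 = 4.01.
- mNGS NPA = 1 − 4.01/192.93 = 97.9%; conventional NPA = 100%. Gap 2.1 points with no true difference.

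At prevalences of 20% and 50% mNGS NPA is again 97.9%. Section 9.4 allows that mNGS may find pathogens other assays cannot yet detect. If only 80% of true mNGS-only positives can be confirmed, mNGS NPA is 97.3%, 96.7% and 95.7% at prevalences of 20%, 35% and 50%.

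**How often some gap appears.** P(at least one unconfirmed mNGS false positive among n reference-negatives) = 1 − specificity^n, treating the reference-negatives as uninfected.

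| Specificity, both tests | n = 150 | n = 200 | n = 250 |
|---|---|---|---|
| 97.9% | 95.9% | 98.6% | 99.5% |
| 99% | 78% | 87% | 92% |
| 99.5% | 53% | 63% | 71% |

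In 20,000 simulated trials of the base case, conventional NPA was 100% every time and mNGS NPA was below 100% in 98.2%.

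**Sensitivity to conventional errors, and PPA.** Hold mNGS fixed and raise only the conventional false-positive rate f. Reference-positives = 105 × (1 − 0.139²) + 195f = 102.97 + 195f. Conventional hits = 90.405 + 195f; mNGS hits = 90.405 + 195f × 0.021.

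| f | Conventional NPA | mNGS NPA | Conventional PPA | mNGS PPA |
|---|---|---|---|---|
| 2.1% | 100% | 97.9% | 94.50/107.07 = 88.3% | 90.49/107.07 = 84.5% |
| 5% | 100% | 97.9% | 100.16/112.72 = 88.9% | 90.61/112.72 = 80.4% |
| 10% | 100% | 97.9% | 109.91/122.47 = 89.7% | 90.81/122.47 = 74.2% |
| 20% | 100% | 97.9% | 129.41/141.97 = 91.1% | 91.22/141.97 = 64.3% |

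Sensitivity is 86.1% for both tests in every row. As conventional testing gets worse, its NPA does not move, its PPA rises and mNGS PPA falls.

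**Interval.** For x = n the Wilson lower limit is n/(n + 1.96²). For 195/195 this is 195/198.84 = 98.1%, so the interval would read 98.1% to 100% around a fixed value. For 191/195 it is 94.8% to 99.2%.

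**Cause.** Requiring confirmation of conventional-only positives as well gives NPA 98.0% and PPA 87.8% for both tests in the base case. The gap comes from one-sided confirmation.

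**The case against.** The strongest reply is that 6.2 never promises a conventional NPA. It names mNGS as the single index test, describes the secondary analyses as PPA and NPA of mNGS, and the synopsis frames the first primary outcome as performance of the mNGS assay. On that reading only mNGS is scored and no 100%-versus-98% contrast arises. This stands in part: a reader might infer that the plan commits the trial to reporting conventional testing as perfectly specific, and the documents do not go that far. But a primary comparison of one test versus the other, on PPA and NPA against a shared reference, invites exactly that row, and nothing excludes it.

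Second, the discrepancy testing in section 9.4 might overturn a conventional positive, in which case conventional NPA could fall below 100%. That is possible, but the testing is framed as a check on mNGS false negatives and the SAP contains no reclassification rule. The 100% result holds on the composite as written.

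Third, 6.2 concedes that unbiased sensitivity and specificity cannot be obtained and adopts agreement terms. That discloses the missing gold standard. It does not disclose that one side of the comparison is fixed, and the change of label leaves the composite as it was.

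Fourth, the 96% to 99.5% figures could be misread as the size of a bias. They are only the chance of at least one unconfirmed mNGS positive; the size is about 2 points. Nor can a false-rejection rate be attached, because 6.2 specifies no hypothesis test.

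**Conclusion.** The point holds in conditional form. On the composite in 6.2, any conventional NPA is 100% by construction unless section 9.4 testing may reclassify conventional positives, and mNGS NPA ties only if every mNGS-only positive is confirmed. This depends on no assumption about prevalence, accuracy or independence.

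The size does depend on assumptions: about 2 percentage points with both specificities at 97.9% and mNGS false positives unconfirmed, and more if true mNGS-only positives cannot be confirmed. Giving conventional testing the mNGS validation specificity has no support in the documents; it only sets up the equal-accuracy case.

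A reader might conclude that dropping NPA and keeping a PPA head-to-head solves the problem. It does not: at equal accuracy the base case already shows PPA of 88.3% against 84.5% in favour of conventional testing. The change is worth making because it affects what the primary comparison can conclude.

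**What to change.** Revise section 6.2 as follows.

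1. Report NPA against the composite for mNGS only, described as agreement.
2. Give no conventional NPA and no Wilson interval for it. State that it is 100% by construction.
3. State that PPA for both tests is affected because conventional positives are accepted unconfirmed: conventional false positives raise conventional PPA and lower mNGS PPA.
4. Draw no conclusion about relative specificity.
5. Base the head-to-head on a paired discordance table: mNGS-only and conventional-only positives, each split into confirmed, not confirmed and not tested.
6. State whether the discrepancy testing in section 9.4 can reclassify a conventional positive and, if so, by what rule.

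The cost is SAP wording and one table from the testing described in sections 8.25 and 9.4 (version 1.16), with no new patients, samples or tests. The trial would no longer state a specificity contrast. Section 8.25 makes no specific provision for retesting conventional-only positives and section 9.4 does so only where judged needed, so many of them may appear as not tested. That is a true account of what was checked.
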